16.10.2. Trademarks

Trademarks of the GlaxoSmithKline Group of Companies
NONE

Trademarks not owned by the GlaxoSmithKline Group of Companies
MedDRA
NONMEM
SAS
WinNonlin

16.11. Appendix 11: List of Data Displays

16.11.1. Data Display Numbering

The following numbering will be applied for RAP generated displays:

Section	Tables	Figures
Study Population	1.0000 to 1.n	1.0000 to 1.n
Efficacy	2.0000 to 2.n	2.0000 to 2.n
Safety	3.0000 to 3.n	3.0000 to 3.n
Pharmacokinetic	4.0000 to 4.n	4.0000 to 4.n
Biomarker	5.0000 to 5.n	5.0000 to 5.n
Health Outcomes	6.0000 to 6.n	6.0000 to 6.n
Section	Listings	
ICH Listings	1.0010 to x	
Other Listings	1.0010 to z	

16.11.2. Mock Example Shell Referencing

Non IDSL specifications will be referenced as indicated and if required example mock-up displays provided in Section [16.12: Example Mock Shells for Data Displays](#).

Section	Figure	Table	Listing
Study Population	POP_Fn	POP_Tn	POP_Ln
Efficacy	EFF_Fn	EFF_Tn	EFF_Ln
Safety	SAFE_Fn	SAFE_Tn	SAFE_Ln
Pharmacokinetic	PK_Fn	PK_Tn	PK_Ln
Biomarker	BIO_Fn	BIO_Tn	BIO_Ln
Health Outcomes	PRO_Fn	PRO_Tn	PRO_Ln

NOTES:

- Non-Standard displays are indicated in the 'IDSL / Example Shell' or 'Programming Notes' column as '[Non-Standard] + Reference.'

16.11.3. Deliverables

Delivery [Priority] ^[1]	Description
IA [1]	Interim Analysis
HDL [2]	Headline results for Primary SAC
P-SAC [3]	Statistical Analysis Complete for Primary Analysis
F-SAC [4]	Statistical Analysis Complete for Final Analysis

NOTES:

- Indicates priority (i.e. order) in which displays will be generated for the reporting effort

16.11.4. Study Population Tables

Study Population Tables					
No.	Population	IDS / Example Shell	Title	Programming Notes	Deliverable [Priority]
Subject Disposition					
1.001	All Treated	ES8	Summary of Subject Status and Reason for Study Withdrawal	Report for: Part 1, Part 2, and combined Part 1 and Part 2; Summarize by: dose level (Refer to Section 5.1 for ordering of dose level and omit 1.92 mg/kg if data is not available) Total; Add the following footnote: "Subject PPD PPD and PP are continuing to Post Analysis Continued Treatment (PACT)."	P-SAC [3], F-SAC [4]
1.002	All Treated	ES8	Summary of Reason for Study Withdrawal by Relationship to COVID-19 Pandemic	Report for: Part 1, Part 2, and combined Part 1 and Part 2; Summarize by: dose level (Refer to Section 5.1 for ordering of dose level and omit 1.92 mg/kg if data is not available) Total; summarise by related to COVID-19 and not related to COVID-19;	P-SAC [3], F-SAC [4]

Study Population Tables					
No.	Population	IDSL / Example Shell	Title	Programming Notes	Deliverable [Priority]
1.003	All Treated	SD1	Summary of Treatment Status and Reasons for Discontinuation of Study Treatment	Report for: Part 1, Part 2, and combined Part 1 and Part 2; Summarize by: dose level (Refer to Section 5.1 for ordering of dose level and omit 1.92 mg/kg if data is not available) Total; Add the following footnote: "Subject PPD and PP are continuing to Post Analysis Continued Treatment (PACT)."	HDL [2], P-SAC [3], F-SAC [4]
1.004	All Treated	SD1	Summary of Reasons for Discontinuation of Study Treatment by Relationship to COVID-19 Pandemic	Report for: Part 1, Part 2, and combined Part 1 and Part 2; Summarize by: dose level (Refer to Section 5.1 for ordering of dose level and omit 1.92 mg/kg if data is not available). summarise by related to COVID-19 and not related to COVID-19; Total;	P-SAC [3], F-SAC [4]
1.005	Screened	ES6	Summary of Screening Status and Reasons for Screen Failure	Report for: Part 1, Part 2, and combined Part 1 and Part 2; Summarize by: dose level (Refer to Section 5.1 for ordering of dose level and omit 1.92 mg/kg if data is not available).	P-SAC [3], F-SAC [4]
1.006	Enrolled	NS1	Summary of Number of Subjects by Country and Site ID	Report for: Part 1, Part 2, and combined Part 1 and Part 2; (Refer to Section 5.1 for ordering of dose level and omit 1.92 mg/kg if data is not available) Total.	P-SAC [3], F-SAC [4]

Study Population Tables					
No.	Population	IDSL / Example Shell	Title	Programming Notes	Deliverable [Priority]
1.007	Screened	BIMO1	Summary of Subject Status in the Study by Country and Site ID	Report for: Part 1, Part 2, and combined Part 1 and Part 2; (Refer to Section 5.1 for ordering of dose level and omit 1.92 mg/kg if data is not available) Total.	P-SAC [3], F-SAC [4]
1.008	Enrolled	NS1	Summary of Number of Subjects by Country and Site ID Relative to COVID-19 Pandemic Measures	Report for: Part 1, Part 2, and combined Part 1 and Part 2; summarise by before and after implementation of pandemic measures; Total	P-SAC [3], F-SAC [4]
Protocol Deviation					
1.009	All Treated	DV1	Summary of Important Protocol Deviations	Report for: Part 1, Part 2, and combined Part 1 and Part 2; Summarize by: dose level (Refer to Section 5.1 for ordering of dose level and omit 1.92 mg/kg if data is not available); Total	P-SAC [3], F-SAC [4]
1.0010	All Treated	DV1	Summary of Important Protocol Deviations by Relationship to COVID-19	Report for: Part 1, Part 2, and combined Part 1 and Part 2; Summarize by: dose level (Refer to Section 5.1 for ordering of dose level and omit 1.92 mg/kg if data is not available) summarise by important related to COVID-19 and important not related to COVID-19; Total	P-SAC [3], F-SAC [4]

Study Population Tables					
No.	Population	IDS / Example Shell	Title	Programming Notes	Deliverable [Priority]
1.0011	All Treated	DV1	Summary of Non-Important COVID-19 Related Protocol Deviations	Report for: Part 1, Part 2, and combined Part 1 and Part 2; Summarize by: dose level (Refer to Section 5.1 for ordering of dose level and omit 1.92 mg/kg if data is not available); Total	P-SAC [3], F-SAC [4]
1.0012	All Treated	IE1	Summary of Inclusion/Exclusion Criteria Deviations	Report for: Part 1, Part 2, and combined Part 1 and Part 2; Summarize by: dose level (Refer to Section 5.1 for ordering of dose level and omit 1.92 mg/kg if data is not available); Total	P-SAC [3], F-SAC [4]
Population Analysed					
1.0013	Enrolled	SP1A	Summary of Study Populations	Report for: Part 1, Part 2, and combined Part 1 and Part 2; Total	P-SAC [3], F-SAC [4]
Demographic and Baseline Characteristics					
1.0014	All Treated	DM1	Summary of Demographic Characteristics	Report for: Part 1, Part 2, and combined Part 1 and Part 2; Summarize by: dose level (Refer to Section 5.1 for ordering of dose level and omit 1.92 mg/kg if data is not available) Total.	HDL [2], P-SAC [3], F-SAC [4]

Study Population Tables					
No.	Population	IDS / Example Shell	Title	Programming Notes	Deliverable [Priority]
1.0015	All Evaluable	DM1	Summary of Demographic Characteristics	Report for: futility interim analyses for part 2 participants and part 1 participants who initially received the RP2D (Refer to Section 5.1 for ordering of dose level). Add the following footnote: A subject is evaluable for interim analysis if the subject fulfils the criteria for 'All Treated' population with adequate baseline assessment and measurable disease meet at least one of the following criteria: if the planned assessment is every 3 weeks and at least three assessments are required, the time from the first dose to the time of data cut-off is more than 66 days, OR had an unconfirmed response of PR/CR or better, progressed, OR died, OR discontinued treatment due to other reasons	IA [1]
1.0016	Enrolled	DM11	Summary of Age Ranges	Include columns "No Treatment", "Part 1", "Part 2", "All Treated", "Total"	P-SAC [3], F-SAC [4]

Study Population Tables					
No.	Population	IDSL / Example Shell	Title	Programming Notes	Deliverable [Priority]
1.0017	All Treated	DM6	Summary of Race and Racial Combinations	Report for: Part 1, Part 2, and combined Part 1 and Part 2; Summarize by: dose level (Refer to Section 5.1 for ordering of dose level and omit 1.92 mg/kg if data is not available) Total.	P-SAC [3], F-SAC [4]
Prior and Concomitant Medications					
1.0018	All Treated	MH1	Summary of Current Medical Conditions	Report for: Part 1, Part 2, and combined Part 1 and Part 2; Summarize by: dose level (Refer to Section 5.1 for ordering of dose level and omit 1.92 mg/kg if data is not available) Total.	P-SAC [3], F-SAC [4]
1.0019	All Treated	MH1	Summary of Past Medical Conditions	Report for: Part 1, Part 2, and combined Part 1 and Part 2; Summarize by: dose level (Refer to Section 5.1 for ordering of dose level and omit 1.92 mg/kg if data is not available) Total.	P-SAC [3], F-SAC [4]
1.0020	All Treated	CM8	Summary of Concomitant Medications by Ingredient	Report for: Part 1, Part 2, and combined Part 1 and Part 2; Summarize by: dose level (Refer to Section 5.1 for ordering of dose level and omit 1.92 mg/kg if data is not available) Total.	P-SAC [3], F-SAC [4]

Study Population Tables					
No.	Population	IDSL / Example Shell	Title	Programming Notes	Deliverable [Priority]
Exposure and Treatment Compliance					
1.0021	All Treated	EX5	Summary of Exposure to Study Treatment	
Report for: Part 1, Part 2, and combined Part 1 and Part 2; Summarize by: dose level (Refer to Section 5.1 for ordering of dose level and omit 1.92 mg/kg if data is not available) Total. Create separate Tables for GSK2857916 and pembrolizumab.
 
Note: to derive actual cumulative dose, use baseline/screening weight in order to capture patients who incorrectly receive the wrong dose for the study treatment .
	HDL [2], P-SAC [3], F-SAC [4]

Study Population Tables					
No.	Population	IDSL / Example Shell	Title	Programming Notes	Deliverable [Priority]
1.0022	All Evaluable	EX5	Summary of Exposure to Study Treatment	
Report for: futility interim analyses for part 2 participants and part 1 participants who initially received the RP2D (Refer to Section 5.1 for ordering of dose level)
 
Add the following footnote: A subject is evaluable for interim analysis if the subject fulfils the criteria for 'All Treated' population with adequate baseline assessment and measurable disease meet at least one of the following criteria: if the planned assessment is every 3 weeks and at least three assessments are required, the time from the first dose to the time of data cut-off is more than 66 days, OR had an unconfirmed response of PR/CR or better, progressed, OR died, OR discontinued treatment due to other reasons
	IA [1]
1.0023	All Treated	OEX9	Summary Listing of Overall Exposure and Dose Modifications	
Report for: Part 1, Part 2, and combined Part 1 and Part 2; Summarize by: dose level (Refer to Section 5.1 for ordering of dose level and omit 1.92 mg/kg if data is not available) Total.
	P-SAC [3], F-SAC [4]

Study Population Tables					
No.	Population	IDSL / Example Shell	Title	Programming Notes	Deliverable [Priority]
Disease Characteristics					
1.0024	All Treated	DC1	Summary of Disease Characteristics at Initial Diagnosis	Report for: Part 1, Part 2, and combined Part 1 and Part 2; Summarize by: dose level (Refer to Section 5.1 for ordering of dose level and omit 1.92 mg/kg if data is not available) Total.	P-SAC [3], F-SAC [4]
1.0025	All Evaluable	DC1	Summary of Disease Characteristics at Initial Diagnosis	Report for: futility interim analyses for part 2 participants and part 1 participants who initially received the RP2D (Refer to Section 5.1 for ordering of dose level) Add the following footnote: A subject is evaluable for interim analysis if the subject fulfils the criteria for 'All Treated' population with adequate baseline assessment and measurable disease meet at least one of the following criteria: if the planned assessment is every 3 weeks and at least three assessments are required, the time from the first dose to the time of data cut-off is more than 66 days, OR had an unconfirmed response of PR/CR or better, progressed, OR died, OR discontinued treatment due to other reasons	IA [1]

Study Population Tables					
No.	Population	IDS / Example Shell	Title	Programming Notes	Deliverable [Priority]
1.0026	All Treated	DC2	Summary of Disease Characteristics at Screening	
Report for: Part 1 and Part 2 and combined Part 1 and Part 2; Summarize by: dose level (Refer to Section 5.1 for ordering of dose level and omit 1.92 mg/kg if data is not available) Total; See Table 1.2101 in 205678 (primary_02) and include footnote for cytogenetics. Include eGFR using DREAMM-2 RE internal_05 T1.11060 (eGFR) collected at baseline with the following categories for eGFR:
 
 • Normal: ≥ 90 • Mild: $\geq 60, < 90$ • Moderate: $\geq 30, < 60$ • Severe: $0, < 30$ • Missing 	HDL [2], P-SAC [3], F-SAC [4]

Study Population Tables					
No.	Population	IDS / Example Shell	Title	Programming Notes	Deliverable [Priority]
1.0027	All Evaluable	DC2	Summary of Disease Characteristics at Screening	
Report for: futility interim analyses for part 2 participants and part 1 participants who initially received the RP2D (Refer to Section 5.1 for ordering of dose level)
 
Add the following footnote: A subject is evaluable for interim analysis if the subject fulfils the criteria for 'All Treated' population with adequate baseline assessment and measurable disease meet at least one of the following criteria: if the planned assessment is every 3 weeks and at least three assessments are required, the time from the first dose to the time of data cut-off is more than 66 days, OR had an unconfirmed response of PR/CR or better, progressed, OR died, OR discontinued treatment due to other reasons
	IA [1]

Study Population Tables					
No.	Population	IDSL / Example Shell	Title	Programming Notes	Deliverable [Priority]
Anti-Cancer Therapy					
1.0028	All Treated	AC2	Summary of Prior Anti-Cancer Therapy	Report for: Part 1, Part 2, and combined Part 1 and Part 2; Summarize by: dose level (Refer to Section 5.1 for ordering of dose level and omit 1.92 mg/kg if data is not available) Total. Refer to mid205678 (primary_08) Table 1.0190 for guidance.	P-SAC [3], F-SAC [4]
1.0029	All Treated	AC2	Summary of Subjects Refractory to Prior Anti-Cancer Therapy	Report for: Part 1, Part 2, and combined Part 1 and Part 2; Summarize by: dose level (Refer to Section 5.1 for ordering of dose level and omit 1.92 mg/kg if data is not available) Total. Refer to mid205678 (primary_08) Table 1.0200 for guidance.	P-SAC [3], F-SAC [4]
1.0030	All Treated	AC3	Summary of Number of Prior Anti-Cancer Therapy Regimens	Report for: Part 1, Part 2, and combined Part 1 and Part 2; Summarize by: dose level (Refer to Section 5.1 for ordering of dose level and omit 1.92 mg/kg if data is not available) Total. Refer to mid205678 (primary_01) Table 1.0220 for guidance.	P-SAC [3], F-SAC [4]

CONFIDENTIAL

205207

Study Population Tables					
No.	Population	IDS / Example Shell	Title	Programming Notes	Deliverable [Priority]
1.0031	All Treated	FAC1	Summary of Follow-up Anti-Cancer Therapy	Report for: Part 1, Part 2, and combined Part 1 and Part 2; Summarize by: dose level (Refer to Section 5.1 for ordering of dose level and omit 1.92 mg/kg if data is not available) Total. Refer to mid205678 (primary_08) Table 1.0240 for guidance.	P-SAC [3], F-SAC [4]
Surgical/Medical Procedures					
1.0032	All Treated	PR1	Summary of Prior Non-Cancer Related Surgical Procedures	Report for: Part 1, Part 2, and combined Part 1 and Part 2; Summarize by: dose level (Refer to Section 5.1 for ordering of dose level and omit 1.92 mg/kg if data is not available) Total..	P-SAC [3], F-SAC [4]
Substance Use					
1.0033	All Treated	SU1	Summary of Substance Use	Report for: Part 1, Part 2, and combined Part 1 and Part 2; Summarize by: dose level (Refer to Section 5.1 for ordering of dose level and omit 1.92 mg/kg if data is not available) Total.	P-SAC [3], F-SAC [4]

Study Population Tables					
No.	Population	IDSL / Example Shell	Title	Programming Notes	Deliverable [Priority]
Follow-up					
1.0034	All Treated	FAC2	Summary of Duration of Follow-up	Report for: Part 1, Part 2, and combined Part 1 and Part 2; Summarize by: dose level (Refer to Section 5.1 for ordering of dose level and omit 1.92 mg/kg if data is not available) Total.	HDL [2], P-SAC [3], F-SAC [4]
Blood and Blood Supportive Care Products					
1.0035	All Treated	BP1A	Summary of Blood Products	Report for: Part 1, Part 2, and combined Part 1 and Part 2; Summarize by: dose level (Refer to Section 5.1 for ordering of dose level and omit 1.92 mg/kg if data is not available) Total.	P-SAC [3], F-SAC [4]
1.0036	All Treated	BP1B	Summary of Blood Supportive Care Products	Report for: Part 1, Part 2, and combined Part 1 and Part 2; Summarize by: dose level (Refer to Section 5.1 for ordering of dose level and omit 1.92 mg/kg if data is not available) Total.	P-SAC [3], F-SAC [4]

16.11.5. Efficacy Tables

Efficacy: Tables					
No.	Population	IDSL / Example Shell	Title	Programming Notes	Deliverable [Priority]
Responses.					
2.001	All Treated	RE1a	Summary of Investigator Assessed Best Response (With Confirmation) (IMWG 2016)	
Report for: Part 1, Part 2, and combined Part 1 and Part 2; Summarize by: dose level (Refer to Section 5.1 for ordering of dose level and omit 1.92 mg/kg if data is not available);
 
Best Response: Stringent Complete Response (sCR), Complete response (CR), Very Good Partial Response (VGPR), Partial Response (PR), Minimal Response (MR), Stable Disease (SD), Progressive Disease (PD), Not Evaluable (NE).
 
Overall Response Rate: (sCR+CR+VGPR+PR).
 
Rate of Very Good Partial Response or better: (sCR+CR+VGPR).
 
Clinical Benefit Rate: (sCR+CR+VGPR+PR+MR).
	HDL [2], P-SAC [3], F-SAC [4]

Efficacy: Tables					
No.	Population	IDSL / Example Shell	Title	Programming Notes	Deliverable [Priority]
				
Include: Overall Response Rate, Rate of VGPR or better and Clinical Benefit Rate (include p-value for the overall response rate for part 2 P-SAC deliverable only) in one table.
 
Include the following footnotes for P-SAC and F-SAC deliverables:
 
“Note: The 95% Confidence Interval is based on Exact method.”
 
Include the following footnotes for P-SAC deliverable:
 
“(1) Probability under the null hypothesis: p=10% of an outcome at least as extreme as that observed.”
	
2.002	All Evaluable	RE1a	Summary of Investigator Assessed Best Response (for Interim Futility Analyses) (IMWG 2016)	
Report for: futility interim analyses for part 2 participants and part 1 participants who initially received the RP2D (Refer to Section 5.1 for ordering of dose level)
 
Add the following footnote: A subject is evaluable for interim analysis if the subject fulfils the criteria for ‘All Treated’ population
	IA [1]

Efficacy: Tables					
No.	Population	IDSL / Example Shell	Title	Programming Notes	Deliverable [Priority]
				with adequate baseline assessment and measurable disease meet at least one of the following criteria: if the planned assessment is every 3 weeks and at least three assessments are required, the time from the first dose to the time of data cut-off is more than 66 days, OR had an unconfirmed response of PR/CR or better, progressed, OR died, OR discontinued treatment due to other reasons.	
2.003	All Treated	See programming notes	Summary of MRD Negativity Rate by Investigator Assessed Best Response	
Report for: Part 1, Part 2, and combined Part 1 and Part 2; Summarize by: dose level (Refer to Section 5.1 for ordering of dose level and omit 1.92 mg/kg if data is not available). MRD negativity will be based on test result with sensitivity of 10^5. Refer to mid205678 (primary_01) Table 2.0040 for guidance. Include the following footnote:
 
Note: Minimal Residual Disease (MRD) negativity rate is defined as: the percentage of participants who are MRD negative by Next Generation Sequencing (NGS). Subjects without MRD assessment
	P-SAC [3], F-SAC [4]

Efficacy: Tables					
No.	Population	IDSL / Example Shell	Title	Programming Notes	Deliverable [Priority]
				will be considered as having positive MRD."	
Time-to-Event Endpoints					
2.004	All Treated	TTE1	Summary of Duration of Response by Investigator (IMWG 2016) (GSK2857916 2.5 mg/kg)	Report for: 2.5 mg/kg doses only; Refer to Section 5.1 and use only code A, code D, and code H for dose level	HDL [2], P-SAC [3], F-SAC [4]
2.005	All Treated	TTE1	Summary of Time to Response by Investigator (IMWG 2016) (GSK2857916 2.5 mg/kg)	Report for: 2.5 mg/kg doses only; Refer to Section 5.1 and use only code A, code D, and code H for dose level	P-SAC [3], F-SAC [4]
2.006	All Treated	TTE1	Summary of Time to Best Response by Investigator (IMWG 2016) (GSK2857916 2.5 mg/kg)	Report for: 2.5 mg/kg doses only; Refer to Section 5.1 and use only code A, code D, and code H for dose level	P-SAC [3], F-SAC [4]
2.007	All Treated	TTE1	Summary of Progression Free Survival by Investigator (IMWG 2016) (GSK2857916 2.5 mg/kg)	Report for: 2.5 mg/kg doses only; Refer to Section 5.1 and use only code A, code D, and code H for dose level; use mid205678(primary_01) T2.0080 for guidance	HDL [2], P-SAC [3], F-SAC [4]
2.008	All Treated	TTE1	Summary of Time to Progression by Investigator (IMWG 2016) (GSK2857916 2.5 mg/kg)	Report for: 2.5 mg/kg doses only; Refer to Section 5.1 and use only code A, code D, and code H for	P-SAC [3], F-SAC [4]

Efficacy: Tables					
No.	Population	IDSL / Example Shell	Title	Programming Notes	Deliverable [Priority]
				dose level	
2.009	All Treated	TTE1	Summary of Overall Survival (GSK2857916 2.5 mg/kg)	Report for: 2.5 mg/kg doses only; Refer to Section 5.1 and use only code A, code D, and code H for dose level; use mid205678(primary_01) T2.0150 for guidance	P-SAC [3], F-SAC [4]
2.0010	All Treated	TTE1	Summary of Time to Next Treatment (GSK2857916 2.5 mg/kg)	Report for: 2.5 mg/kg doses only; Refer to Section 5.1 and use only code A, code D, and code H for dose level	P-SAC [3], F-SAC [4]

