2.4.2. Part 2: Expansion Cohort

The primary goal of Part 2 is to characterize clinical activity of the combination and to detect if meaningful response rate (ORR) can be achieved. Based on historical information [[Lokhorst](#), 2015] and clinical judgement, the null hypothesis has been defined as $ORR \leq 40\%$. The alternative hypothesis has been defined as $ORR \geq 60\%$ based on clinically meaningful improvement of 20%.

In Part 2, treatment-related Grade 4 or higher AEs will be continuously monitored starting from when 5 participants are dosed. Based on the 11% Grade 4 or higher AEs observed in the FTIH study (BMA117159), it is considered that the combination treatment has unacceptable toxicity if observed treatment-related Grade 4 or higher AEs is significantly higher than 12% at 1-sided alpha of 0.025.

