3.1.2.1. Operating Characteristics of the Stopping Rules for Futility

The futility stopping rule in Table 3 is based on the methodology of Lee et al. [Lee, 2008]. The optimal design has a maximum sample size of 28 and a type I error rate of 0.10 and power of 80.6%. The expansion cohort may be stopped early for futility if the predicted probability of success is less than 1.5%. Under the null hypothesis, if the true ORR is 40%, the expected sample size of the design is 20 subjects and probability of early termination is 86.1%. Under the alternative hypothesis, if the true ORR is 60%, the expected sample size is 28 and the probability of early termination is 15.6%.

Table 3 Decision Making Criteria for Futility Analysis

Number of Evaluable Subjects	\leq This Number of Responses to Stop Early for Futility	Probability of continuing enrolling when ORR=0.4	Probability of continuing enrolling when ORR=0.6
10	2	83.3%	98.8%
11	2	83.3%	98.8%
12	3	75.5%	98.1%
13	3	75.5%	98.1%
14	4	68.6%	97.5%
15	4	68.6%	97.5%
16	5	62.3%	96.9%
17	6	52.9%	95.7%
18	6	52.9%	95.7%
19	7	46.7%	94.9%
20	7	46.7%	94.9%
21	8	41.6%	94.2%
22	9	34.6%	92.8%
23	9	34.6%	92.8%
24	10	30.2%	91.9%
25	11	24.4%	90.2%
26	12	18.8%	87.7%
27	13	13.9%	84.5%
28	14	0.0%	0.0%

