7.1.1.2. Summary Measure

ORR

The number and percentage of participants with the BOR in the following response categories at timepoint will be summarized: sCR, CR, VGPR, PR, overall response (sCR+CR+VGPR+PR), minimal response (MR), stable disease (SD), progressive disease (PD), and not evaluable (NE). The corresponding exact 95% CI for ORR will also be provided. Participants with unknown or missing responses will be treated as non-responders, i.e., these participants will be included in the denominator when calculating percentages of response. A list of investigator-assessed response at each visit will be listed.

A waterfall plot showing the maximum percent reduction from baseline in Serum M protein, or Urine M-protein, or difference between two types Serum FLC [Kappa light chain (Kappa LC) and Lambda light chain (Lambda LC)] for each subject will be produced using by dose level. The plot will be color-coded for M-protein types and Serum FLC, etc. Indication of the best overall response will be provided below the plot. Only the assessments from the start of treatment up to the start of new anti-cancer therapy will be considered. Only new systemic anti-cancer drugs taken are considered as anti-cancer cancer therapy (radiotherapy and surgeries are not considered as systemic anti-cancer therapy for the purpose of this analysis).

The maximum percent reduction will be plotted in the following hierarchical order:

- [1] Plot Serum M-protein maximum percent reduction from baseline if data is available;
- [2] If [1] is not feasible, plot Urine M-protein maximum percent reduction from baseline if data is available;
- [3] If both [1] and [2] are not feasible, plot maximum percent reduction from baseline for difference between two types of Serum FLC if data is available;

Difference between two types of Serum FLC

The percent change from baseline for difference between two types of Serum FLC is defined as:

$$(\text{post-baseline difference} - \text{baseline difference}) / \text{baseline difference} * 100\%$$

To calculate the difference, the “involved” and “non-involved” light chains must be determined at first based on the ratio of non-missing values for Serum Kappa LC protein and Serum Lambda LC protein at baseline.

The detailed algorithm is provided as below:

- If the baseline ratio of (Kappa LC/Lambda LC)>1.65, then Kappa LC is defined as involved FLC, and Lambda LC is defined as non-involved FLC. Then

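### The p-value ordered for the Part 2 ORR at the primary analysis is labelled with a 10% null, although the trial's null hypothesis is ORR of 40% or less

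*SAP*

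**What the plan says.** Section 2.4.2 of the SAP sets the Part 2 null hypothesis at an ORR of 40% or less and the alternative at 60% or more.

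Section 3.1.2.1 builds the design on those values: "The optimal design has a maximum sample size of 28 and a type I error rate of 0.10 and power of 80.6" percent. The operating characteristics are given first at the null ("Under the null hypothesis, if the true ORR is 40" percent) and then at 60%. The last row of Table 3 puts 14 or fewer responses among 28 on the failing side, so success needs at least 15.

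Sections 7.2.1.1 to 7.2.1.4, on the primary efficacy analysis, refer back to the ORR definition and summary and otherwise promise descriptive statistics. They name no test, null value or level.

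The p-value appears only in the programming note to Table 2.001 in Section 16.11.5. It is to be shown for the Part 2 ORR, in the primary-analysis (P-SAC) deliverable only, with the footnote "Probability under the null hypothesis: p=10% of an outcome at least as extreme as that observed".

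**The concern.** The footnote defines what the p-value measures. A p-value against 10% answers whether the response rate exceeds 10%, which this trial does not ask. A programmer who follows the note would compute the wrong tail probability for the primary endpoint, and nothing in Section 7.2.1 would stop it.

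The error also runs in the favourable direction. Rates that fall well short of the design's success threshold, and even rates below the 40% null, lie far above 10%. They would be printed with a small p-value beside the primary result.

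**Working it through.** **Inputs.** Null 40% and alternative 60% (Section 2.4.2). Maximum n = 28, type I error 0.10, power 80.6% and the Table 3 boundary (Section 3.1.2.1). Null value in the p-value footnote: 10% (Section 16.11.5, Table 2.001).

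**Step 1: which null does the design use?** I ran an exact binomial recursion through Table 3, removing every path at or below the boundary at n = 10 to 27 and counting success at 15 or more of 28.

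| Quantity | SAP | Recomputed |
|---|---|---|
| Rejection probability at ORR 40% | 0.10 | 0.0997 |
| Rejection probability at ORR 60% | 80.6% | 80.55% |
| Early termination at ORR 40% | 86.1% | 86.1% |
| Early termination at ORR 60% | 15.6% | 15.5% |

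The continuation probabilities for n = 10 to 27 in Table 3 also reproduce, to rounding. At a true ORR of 10% the same rule would reject with probability about 1e-8. The stated level of 0.10 therefore belongs to a 40% null, one-sided.

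**Step 2: the p-value under each null.** The one-sided exact p-value for r responses is P(X ≥ r) = Σ C(28,k) p0^k (1 − p0)^(28 − k), summed over k = r to 28.

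| Responses of 28 | p against 10% | p against 40% | Table 3 |
|---|---|---|---|
| 5 | 0.142 | 0.997 | failure |
| 6 | 0.055 | 0.989 | failure |
| 7 | 0.018 | 0.969 | failure |
| 12 | 6.5e-6 | 0.449 | failure |
| 14 | 1.0e-7 | 0.187 | failure |
| 15 | 1.0e-8 | 0.1025 | success |
| 16 | 9.3e-10 | 0.050 | success |

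The 14-of-28 row is the cleanest illustration. It can be reached even with every futility stop obeyed (14 of 27, then a non-responder), and the design calls it a failure.

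**Step 3: how often would a treatment at the null look significant?** Take a true ORR of 40%.

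- *All 28 enrolled whatever the interims show.* p<0.05 against 10% needs at least 7 responses: P(X ≥ 7 | 28, 0.40) = 0.969, or 97%.
- *Every futility stop obeyed.* A stop at 2 of 10 gives p = 0.264 against 10%, and a stop at 3 of 12 gives 0.111. The next possible stop, 4 of 14, gives 0.044, and all later stops give less. So p<0.05 occurs exactly when the trial continues past 12 subjects. Table 3 puts that probability at 75.5%, about 76%. Subtracting the 10.0% that reach success leaves about 66% that are both p<0.05 in the table and failures by the design.

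**Step 4: does correcting the null suffice?** Not quite. At 15 of 28, the smallest success, the fixed-sample exact p-value against 40% is 0.1025, just above 0.10. The design's 0.0997 is lower because some paths that would have reached 15 are stopped earlier for futility. At that one result the boundary and the p-value disagree, so the plan has to say which governs.

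**The case against.** The strongest reply is that this is a one-line slip in a programming note and the design is intact. Much of that stands. Table 3 is calibrated to 40%, and the futility decisions do not use the footnote. The 10% may be the type I error rate entered in the wrong place, or a value left over from another table; the SAP does not say. Under any of these explanations, though, the printed null disagrees with Section 2.4.2, and no other text in the SAP corrects it.

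The size of the effect also depends on conduct. With the stops obeyed, 7 of 28 cannot occur, because the trial would have stopped earlier, and the 97% figure does not apply. Stopping is advisory in Section 3.1.2, so the truth lies between that figure and 76%. Very poor results would not look significant at all: 2 of 10, 3 of 12 and 6 of 28 all give p above 0.05 against 10%.

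A reader might infer three stronger things that the SAP does not support:

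- *That the error reaches the headline results.* Table 2.001 is part of that deliverable, but the note restricts the p-value to P-SAC.
- *That the primary question is left without any valid assessment.* The last row of Table 3 still gives a boundary based on 40%, and the interval lets a reader compare the observed ORR with 40%.
- *That the planned interval is a second error.* Section 7.1.1.2 says "The corresponding exact 95% CI for ORR will also be provided", and Section 7.2.1.2 carries this over to Part 2. A 95% interval beside a 0.10-level design is an ordinary estimate. The SAP never makes it a success criterion, so judging it by the power of such a rule would fault something the plan does not propose.

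**Conclusion.** The footnote is wrong as written. The p-value it defines for the primary endpoint tests 10%, while the stated hypothesis and the whole Part 2 calibration use 40%. Results the design treats as failures would be reported as highly significant, with 14 of 28 the clearest case (about 1e-7 instead of 0.187). At a true ORR of 40%, p<0.05 against 10% would appear in about 76% to 97% of trials, depending on whether the futility stops are followed.

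These figures assume a one-sided exact binomial p-value computed on the subjects enrolled when the trial ends. They also assume that the same responses count at the interims and at the primary analysis, and that all subjects belong to Part 2. The SAP counts unconfirmed responses at the interims and lets Part 1 subjects at the RP2D into them, so the 76% is approximate. The fixed-sample p-values in Step 2 do not depend on those last two assumptions. The damage is confined to the reported p-value and its label; the go/no-go rule stands.

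**What to change.** 1. In the Table 2.001 footnote (Section 16.11.5), change the null from 10% to 40%.
2. In Section 7.2.1.4, name the test: one-sided exact binomial of ORR ≤ 40% at the 0.10 level, for the Part 2 subjects.
3. In the same place, state that the Table 3 boundary, at least 15 of 28 responses, decides success and that the p-value is reported alongside it. Give the reason: the exact p at 15 of 28 is 0.1025, while the design's level is 0.0997 only when futility stops are obeyed.

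The planned 95% interval can stay as it is, and no further interval is needed. The cost is one programming note and a few lines of SAP text, with no change to sample size or data collection. The reported p-value will be much less favourable than the one now specified.
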